3.5. Ankle Accelerometry Analysis Set

The ankle accelerometry analysis set is a subset of the mITT analysis set that will include patients who wore an ankle accelerometer with sufficient memory to capture 12 weeks of data during study participation and for whom data from the ankle accelerometer were successfully downloaded at the end of the study.

4. GENERAL ISSUES FOR DATA ANALYSIS

4.1. General

Descriptive statistics for continuous variables include n (number), mean, standard deviation (SD), median, minimum, and maximum. Minimum and maximum will have the same number of decimal points as the original data. Mean and median will have 1 more decimal point than the original data. Reporting of SD will have 2 more decimal points than the original data.

Descriptive statistics for categorical variables include patient counts and/or counts and percentages. Categories for missing data will be presented, if necessary. Confidence intervals (CIs) of means and/or proportions will be reported as specified. Summaries will be provided overall and by CAE status (CAE: No, CAE: Yes, All) and by CAE severity (Yes: Moderate, Yes: Severe) where appropriate.

4.2. Specification of Baseline Values

4.2.1. Albuterol Use

For the purpose of the analysis described in Section 7.1.2.1, baseline albuterol use is defined as no more than 4 inhalations (eg, 0 to 4 inhalations) per day of use regardless of the number of days albuterol is used in a 7-day period. Of note, the term ‘baseline’ does not refer to study days -14 to 1 of study, but rather to the expected daily albuterol use of asthma symptoms that is controlled.

4.2.2. Vital Signs, Physical Examination, Height, and Weight

Baseline vital signs (systolic blood pressure, diastolic blood pressure, respiratory rate, and heart rate (pulse rate), physical examination, height, and weight are performed only at Screening. Given the screening and baseline visits can be combined, baseline vital signs, physical examination, height, and weight are those assessments performed during the Screening visit.

4.2.3. Inhalational Flow Values

The baseline inspiratory flow values are computed using the set of inhalations taken by the patient during study day 1 through day 14. Among these inhalations, the inhalation with the highest maximal inhalation flow (MIF) value is considered the ‘baseline inhalation’. The baseline MIF, inhalational volume, inhalation duration, and time to MIF values are those of the identified ‘baseline inhalation’. If no inhalations were taken during study day 1 through study day 14, the ‘baseline inhalation’ is the first available inhalation after study day 14.

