 Patients may be enrolled in this study only if they meet all of the following criteria: a. The patient is male or female, 18 years of age or older, with a physician diagnosis of uncontrolled asthma. b. The patient has had at least 1 episode of severe CAE (requiring an emergency department visit or hospitalization) as described in Section 6.1.1 over the past 12 months before screening. 	 Patients may be enrolled in this study only if they meet all of the following criteria: a. The patient is male or female, 18 years of age or older, with a physician diagnosis of asthma. b. The patient has had at least 1 episode of severe CAE as described in Section 6.1.1 over the past 12 months before screening. 	Inclusion Criterion a was changed because the original intent was to include the entire asthma population. Inclusion Criterion b was changed to reflect the change made to the definition of CAE.		
Section 4.2 Exclusion Criteria				
d. The patient has or has had CAE within 4 weeks of baseline.	d. [Criterion deleted]	Exclusion Criterion d was deleted because the risk of CAE is highest in the 30-day period following an exacerbation, and their pattern of albuterol use is of great interest from the research and clinical perspective.		

Original text with changes shown	New wording	Reason/justification for change		
Section 5.1 Investigational Medicinal Products Used in the Study				
Patients will be instructed on the proper use of the device, including the requirement for use within 60 seconds of opening the cap.	Patients will be instructed on the proper use of the device, including the requirement for use within 60 seconds of opening the cap.	This change was made to specify the need to use the device within 60 seconds of opening the cap or it will time out, and no inhalation data will be collected.		
Section 5.1 Investigational Medicinal Products Used in the Study (Table 2 Investigational Medicinal Products Used in the Study)				
Packaging: IMP will be provided in a foil pouch within a box	Packaging: IMP will be provided in a box	Language was updated to correct the description of the packaging of IMP		
Section 5.2.1 Storage and Security				

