4.2.4. Total Daily Steps

Baseline TDS is the average number of daily steps a patient completes, computed using the daily steps recorded during the first 14 days of study participation (study day 1 through study day 14). The average will be calculated as the sum of the daily TDS divided by the number of days with nonmissing TDS. If no step data are available for study day 1 through study day 14, the ‘baseline TDS’ is the first available TDS after study day 14.

Baseline TDS are computed for those patients in the ankle accelerometry analysis set.

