4.2.5. Sleep Parameters

There are 8 measures of sleep disruption: (i) nighttime average total time in bed, (ii) nighttime average total sleep time, (iii) nighttime average sleep latency time, (iv) nighttime average wakening after sleep onset, (v) total time awake at night, (vi) daytime average minutes asleep, (vii) longest daytime sleep episode and (viii) longest nighttime wake episode. The first 7 sleep parameters are provided via Philips accelerometry and longest nighttime wake episode is derived from the accelerometry data as follows:

The sleep interval data provided via Philips accelerometry includes the activity state ("sleep"/"awake") every 30 seconds during the sleep interval. The number of successive 30 second "awake" states occurring between "sleep" states within the sleep interval is summed to determine the duration of a given "awake" state. The longest nighttime wake episode is the summated "awake" state with the longest duration during the sleep interval.

The baseline value of a given sleep parameter (eg, nighttime average total time in bed) is the average sleep parameter (eg, nighttime average total time in bed), computed using the sleep parameter (eg, nighttime average total time in bed) values captured by accelerometry during study day 1 through day 14. The average will be calculated as the sum of the average sleep parameter divided by the number of days with nonmissing values of the average sleep parameter. If no sleep parameter data are available for study day 1 through study day 14, the 'baseline value of a given sleep parameter' is the first available valid sleep parameter value after study day 14.

Baseline sleep parameters are computed for those patients in the wrist accelerometry analysis set.

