7.5.2.1. Within Patient CAE Analyses

For each CAE event occurring at least 2 weeks after baseline, device-use measures (albuterol use, inhalational flow [MIF], inhalational volume, and time to MIF) will be summarized for each of 2 weeks of interest: first- 'CAE-adjacent week', the week immediately preceding the onset of CAE symptom (ie, day 1 through 7 preceding the date of the CAE symptom onset), and second – 'CAE-Prior Adjacent week', the week preceding that week (ie, during day 8 through 14 preceding the date of the CAE symptom onset). Summary measures of daily and or weekly use will be compared between the two weeks, as proposed below:

Albuterol use measures:

- total number of inhalations in that week
- the maximal daily number of inhalations in that week
- the mean number of daily inhalations (ie, total number of inhalations divided by number of days with number>0)
- occurrence of a single day's albuterol use exceeding 4 inhalations;
- occurrence of a single day's albuterol use exceeding 8 inhalations
- occurrence of a single day's albuterol use exceeding 12 inhalations
- number of days when albuterol use exceeding 4 inhalations;
- number of days when albuterol use exceeding 8 inhalations
- number of days when albuterol use exceeding 12 inhalations

To note, in this analysis, no inhalation in any day will be taken as a 0 count.

Inhalation flow values parameters:

- maximal daily MIF during the week
- minimal daily time to MIF within a week
- maximal total daily inhalational volume within a week,

To note, if no inhalation was taken at a specific day, flow value parameters will be missing and will not be imputed.

Analysis will be based on all patients CAEs for which there are 14 days (or more) prior to the CAE onset, where patient has been on study and CAE free.

Descriptive statistics of use measures in the 'CAE-adjacent week' and 'CAE-Prior Adjacent week' will be presented.

Continuous measures will be compared between the 2 weeks using paired t-test (and Wilcoxon Signed Ranks test) whereas binary patterns will be compared using Mc-Nemar test.

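### The flow, step and sleep baselines can contain an early CAE, its run-up or its recovery, which distorts the descriptive change-from-baseline tables for early CAEs

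*SAP*

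**What the plan says.** For flow, SAP 4.2.3 states: "The baseline inspiratory flow values are computed using the set of inhalations taken by the patient during study day 1 through day 14". Among these, "the inhalation with the highest maximal inhalation flow (MIF) value is considered the" baseline inhalation, and its four flow values become the baseline. SAP 4.2.4 averages daily steps over the same 14 days, and SAP 4.2.5 averages sleep "values captured by accelerometry during study day 1 through day 14".

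Each section has a fallback. For steps: "If no step data are available for study day 1 through study day 14", the baseline "is the first available TDS after study day 14". Flow and sleep have parallel rules. None of the three sections mentions CAEs.

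Under SAP 4.5, day 1 is the first device dispensing, and SAP 7.5.1 times CAEs from that day. The baseline window is therefore at-risk follow-up and not a run-in.

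SAP 7.2.2.1 (flow), 7.3.2.1 (steps) and 7.4.2.1 (sleep) report actual values and change from baseline at 1, 3, 5, 7, 10, 14 and 21 days before the symptom peak, for all CAEs. The multiple-CAE rules in 7.2.2.1 and 7.3.2.1 deal with overlap between CAEs, not with overlap with the baseline window.

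Only SAP 7.5.2.1 restricts early events, requiring "14 days (or more) prior to the CAE onset, where patient has been on study and CAE free". That analysis compares two weeks before onset and does not use these baselines. SAP 8 plans no sensitivity analysis.

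**The concern.** A change from baseline before a CAE is informative only if the baseline describes the patient away from the CAE. Here an early CAE can place its deterioration, peak or recovery inside the reference value. The look-back day can also be one of the days that make up the baseline.

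Early CAEs are possible by design, because Protocol 4.2 does not exclude patients with a recent exacerbation. That is a legitimate enrolment choice, but it does not make days 1-14 a clean reference.

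At stake is the description of whether flow, steps and sleep move before a CAE. For steps and sleep, 7.3.2.1 and 7.4.2.1 are the only pre-CAE analyses that the SAP specifies. SAP 7.5.2.1 covers albuterol and flow only, and 7.5.3 leaves predictive modelling to a separate report.

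**Working it through.** **Inputs.** Evaluable patients 360, CAE rate 20% to 25% (SAP 2.3). Follow-up 12 weeks = 84 days (SAP 2.1). Accelerometer subsets of 100 each (SAP 1.1). Pre-CAE changes seen up to 10 days before a CAE and well established at 5 days (Protocol 3.3, from a cited descriptive study).

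**Plan's own figure.** 400 × 0.90 = 360; 360 × 0.20 = 72; 360 × 0.25 = 90. The planned 72 to 90 CAEs are reproduced.

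**Peaks in the window.** The documents give no timing of CAEs, so I assume peaks evenly spread over days 1-84.
- All patients: 14/84 = 16.7%; 72 × 14/84 = 12 and 90 × 14/84 = 15.
- Each subset: 100 × 0.20 to 0.25 = 20 to 25 CAEs, of which 20 × 14/84 = 3.3 to 25 × 14/84 = 4.2 peak in the window.
- If risk in the first 30 days were m times higher (assumption), the share is 14m/(30m + 54): 21/99 = 21% for m = 1.5 and 42/144 = 29% for m = 3.

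**Run-up in the window.** With a 10-day run-up, a peak on day 24 has run-up days 14-23, so day 14 is still touched; a peak on day 25 is clear. Peaks by day 24: 24/84 = 29%.

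**Look-back day in the window.** I read the tables as values on the single day L days before the peak. A CAE contributes only if it peaks after day L (84 − L peak days). Its look-back day is in days 1-14 for peaks on days L+1 to L+14, always 14 peak days. The last column is the loss when peaks must also fall after day 24.

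| L | Contributing peak days | Look-back day in window | Excluded if peak must also be after day 24 |
|---|---|---|---|
| 1 | 83 | 14/83 = 17% | 23/83 = 28% |
| 3 | 81 | 14/81 = 17% | 21/81 = 26% |
| 5 | 79 | 14/79 = 18% | 19/79 = 24% |
| 7 | 77 | 14/77 = 18% | 17/77 = 22% |
| 10 | 74 | 14/74 = 19% | 19% (unchanged) |
| 14 | 70 | 14/70 = 20% | 20% (unchanged) |
| 21 | 63 | 14/63 = 22% | 22% (unchanged) |

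For flow these shares are a floor. SAP 7.2.1 carries the last inhalation forward to days without use, so a look-back day after day 14 can carry an in-window value.

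**Steps and sleep.** Let the usual level be μ and the run-up level μ + δ. With r run-up days in a full 14-day mean, the baseline is μ + rδ/14. The reported change on a run-up day is then δ(1 − r/14): 9/14 = 64% of δ for r = 5 and 4/14 = 29% for r = 10. This takes δ as constant over the run-up.

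**Flow.** Baseline MIF is the highest in the window, and the daily value (SAP 7.2.1) is the highest of that day. For a day inside the window the daily value cannot exceed the baseline, so the MIF change is zero or negative whatever happened clinically.

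**Fallback.** Suppose a patient has no step data on days 1-14, first data on day 19, and a CAE peaking on day 20. Day 19 is both the baseline and the 1-day look-back, so the change is exactly zero. The same holds for flow if only one inhalation was taken that day. A fallback taken after a CAE becomes the reference for later CAEs and for the weekly and albuterol-threshold tables.

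**The case against.** Several stronger readings are tempting, and the documents do not support them.

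- *Overlap of 25%, 33% or 42% at 7, 14 and 21 days.* A reader might compute (14 + L)/84. That counts peaks on days 1 to L, whose look-back day precedes day 1 and has no data. The shares of contributing CAEs are 18%, 20% and 22%.
- *Bias always towards no change.* This fits the step and sleep means. It does not fit MIF, where the best-inhalation rule tends to pick the least affected inhalation and can build in a fall.
- *A post-CAE fallback reverses that CAE's change.* If the first available value comes after the CAE, there is no pre-peak value and the change is missing. The harm falls on later CAEs and the other tables.
- *The protocol shows that CAEs cluster early in the study.* The Amendment 01 rationale says "the risk of CAE is highest in the 30-day period following an exacerbation", which is risk after an exacerbation and not after study entry. Protocol 4.1 asks only for a severe CAE in the past 12 months, and the share with a recent one is not given. Front-loading is therefore an assumption.

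The other side also has sound points on consequence. The affected tables are descriptive, and actual values are already planned beside the changes. The albuterol t-test (SAP 7.1.2.3) and the paired-week tests (7.5.2.1) do not use these baselines, so the formal flow comparison is protected. Each accelerometer subset would have only about 3 to 4 CAEs peaking in the window.

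These points limit the weight of the concern but do not remove it. The protection in 7.5.2.1 does not extend to steps or sleep, and with 20 to 25 CAEs per subset a few distorted changes can matter to a mean.

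**Conclusion.** The concern holds in a limited form. Followed exactly, the SAP gives distorted changes from baseline for a minority of CAEs. Under even spread, 17% peak inside the window, 17% to 22% of contributing CAEs have the look-back day inside it, and up to 29% can contaminate the baseline if the run-up lasts 10 days. For steps and sleep the distortion is dilution. For MIF it is a change that cannot be positive on in-window days. A fallback baseline can give an exact zero.

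The percentages rest on even spread of peaks and on the single-day reading of the look-back. The dilution figures also need a constant run-up shift and 14 non-missing days. No hypothesis test is affected. The change should be made, but the study's main comparisons do not depend on it.

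**What to change.** 1. In SAP 7.2.2.1, 7.3.2.1 and 7.4.2.1, present change from baseline only for CAEs whose look-back day is after day 14, in patients CAE-free on days 1-14. For flow, apply this to the date of the inhalation actually used, because of the carry-forward.
2. In SAP 4.2.3 to 4.2.5, and where SAP 4.6 restates the fallback, do not accept a fallback baseline on or after the onset of a CAE. Also bar one from the same day as the look-back value.
3. Repeat the change tables for CAEs peaking after day 24. Rule 1 alone admits a CAE peaking on day 16 at the 1-day look-back, although days 6-14 of its baseline (9 of 14 days) lie in a 10-day run-up.
4. Keep actual values for all CAEs, as planned.

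The cost is SAP wording, which SAP 2.4.2 allows before database lock. Rule 1 removes about 17% to 22% of contributing CAEs from the change tables, plus later CAEs in patients with an early one, for which the documents give no figure. The repeat removes 22% to 28% at look-backs of 1 to 7 days and no more than rule 1 at 10 days or longer.

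One limit remains. Comparing a 14-day maximum with a single day's maximum favours an apparent fall in MIF on days after day 14 too. With no true change, independent normal values and daily use, the mean change was −1.70, −1.45 and −1.27 SD for 1, 2 and 4 inhalations a day, about the same inside and outside the window. The MIF tables should carry a note saying so.

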4.5. Study Day and Study Week

Study days will be numbered relative to the earliest date an ABS eMDPI device was dispensed (ie, ... -2, -1, 1, 2, ...). Day 1 is defined as the earliest date an ABS eMDPI device was dispensed and Day -1 is the day before the first ABS eMDPI device was dispensed.

Week I is defined as study day $(j + 1)$ to study day $(j + 7)$, inclusive where $I = 1$ to 12 and $j = 0, 7, 14, 21, 28, 35, 42, 49, 56, 63, 70, 77, 84$, respectively.

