4.6. Handling Withdrawals and Missing Data

Any data that was collected prior a patient's withdrawal from the study will be used for analysis and presented in the data listings.

The following imputation rules will be used;

- If the return date of the last ABS eMDPI device returned is missing the patient's last date of contact or study completion date will be used as the return date (see Section 4.4 and Section 10.2).
- Adverse events or serious adverse events with missing start dates will be considered treatment emergent (see Section 10.4).
- If a patient never used the ABS eMDPI during the study or download of a given ABS eMDPI device was not successful, study day and weekly inhalational flow values will be missing. If download of a given wrist or ankle accelerometer was not successful, TDS and SDI indices will be missing. These missing data will not be imputed.
- In the derivation of Study Day X Inhalation flow values, if there was no albuterol use on Study Day X , then the closest preceding nonmissing Study Day Inhalation' is used as the 'Study Day X Inhalation' and the inhalational flow values for Study Day X are assigned accordingly (see Section 7.2.1).
- For patients in the ankle accelerometry analysis set if no step data are available for study day 1 through study day 14, the 'baseline TDS' is the first available TDS after study day 14 (see Section 4.2.4).
- For patients in the wrist accelerometry analysis set if no sleep parameter data are available for study day 1 through study day 14, the 'baseline value of a given sleep parameter' is the first available valid sleep parameter value after study day 14 (see Section 4.2.5).

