7.2. Inhalational Flow Values

7.2.1. Inhalational Flow Values Definitions

Study Day X and Week Y inhalational flow values are defined as follows:

Study Day X Inhalational Flow Values: The inhalational flow values for Study Day X are computed using the set of inhalations taken by the patient on Study Day X . Among these inhalations, the inhalation with the highest MIF value is considered the 'Study Day X Inhalation'. The Study Day X MIF, inhalational volume, inhalation duration, and time to MIF values are those of the identified 'Study Day X Inhalation'. If there was no albuterol use on Study Day X ,

then the closest preceding nonmissing Study Day Inhalation' is used as the 'Study Day *X* Inhalation' and the inhalational flow values for Study Day *X* are assigned accordingly.

Week *Y* Inhalational Flow Values: The inhalational flow values for Week *Y* are computed using the set of inhalations taken by the patient during a given week on the study. Among these inhalations, the inhalation with the highest MIF inhalation flow value is considered the 'Weekly *Y* Inhalation'. The Weekly *Y* MIF, inhalational volume, inhalation duration, and time to MIF values are those of the identified 'Weekly *Y* Inhalation'.

Note, if a patient never used the ABS eMDPI during the study or download of a given ABS eMDPI device was not successful, study day and weekly inhalational flow values will be missing.

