7.2.2. Analysis Methods for Inhalational Flow Values

7.2.2.1. Actual and Change from Baseline in Study Day *X* Inhalational Flow Values Prior to the Peak of a CAE

Among patients who experienced a CAE, summary descriptive statistics of the actual inhalational flow values and change from baseline in daily inhalational flow values for MIF, inhalational volume, inhalation duration, and time to MIF at 1 day (eg, the 24-hour period on the day prior to the date of the CAE symptom peak) and at 3, 5, 7, 10, 14, and 21 days preceding the peak of a CAE will be presented for all CAEs and by moderate CAEs and severe CAEs.

In this analysis, among patients experiencing more than 1 CAE, the subsequent CAEs can be considered a separate CAE distinct from the first (preceding) CAE provided the patient exhibited at least 1 day of baseline albuterol use after the first (preceding) CAE's date of symptom peak and prior to the subsequent CAE's date of symptom peak. For patients who experience multiple CAEs (eg, 3), for a given number of days preceding a CAE (eg, 7 days), if the (eg, third) CAE overlaps with the time period of the preceding (eg, second) CAE, the CAE (eg, third CAE) should not be included in the analysis.

Summary descriptive statistics of the actual inhalational flow values and change from baseline in daily inhalational flow values for MIF, inhalational volume, inhalation duration, and time to MIF will be presented for the first occurrence of a single day's albuterol use exceeding (i) 4 inhalations, (ii) 12 inhalations, and (iii) 20 inhalations, overall and by CAE status and by CAE severity.

In addition, summary descriptive statistics of the maximum change from baseline in daily inhalational flow values for MIF, inhalational volume, inhalation duration, and time to MIF will be presented overall and by CAE status and by CAE severity.

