7.2.2.2. Actual and Change from Baseline in Week *Y* Inhalational Flow Values

Summary descriptive statistics of the actual inhalational flow values and change from baseline in MIF, inhalational volume, inhalation duration, and time to MIF for each study week (1 through 12) will be presented overall, and by CAE status and by CAE severity.

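### In the SAP's single-day and weekly change-from-baseline tables, MIF and weekly longest nighttime wake are set against baselines built differently, so the expected change is not zero when nothing has changed

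*SAP*

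**What the plan says.** **Flow.** Under SAP 4.2.3, among all inhalations of study days 1 to 14, "the inhalation with the highest maximal inhalation flow (MIF) value is considered the" baseline inhalation, and all four flow parameters are read from it. With no use in those 14 days, baseline is the first later inhalation. Under 7.2.1, Study Day X values "are computed using the set of inhalations taken by the patient on Study Day" X, again keeping the one with the highest MIF. For Week Y, "the inhalation with the highest MIF inhalation flow value is considered the" inhalation of that week. On a day without use, "then the closest preceding nonmissing Study Day Inhalation" is carried forward (4.6, 7.2.1).

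**Flow tables.** Section 7.2.2.1 plans "summary descriptive statistics of the actual inhalational flow values and change from baseline in daily inhalational flow values for MIF" and the other flow parameters at 1 to 21 days before the exacerbation peak. It repeats them for the first day of "albuterol use exceeding (i) 4 inhalations, (ii) 12 inhalations, and (iii) 20 inhalations, overall and by CAE status" and severity, and adds a maximum change from baseline. Section 7.2.2.2 gives actual values and changes from MIF through "time to MIF for each study week (1 through 12) will be presented overall, and by CAE status and by CAE severity". In section 4.5, "Week I is defined as study day" j + 1 to j + 7. With j = 0 and 7, Weeks 1 and 2 are exactly days 1 to 14.

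**Sleep.** The baseline of each sleep parameter, including longest nighttime wake, is a mean over nonmissing nights of days 1 to 14 (4.2.5). The Week Y longest wake is the greatest value of the week, while weekly sleep latency and total time awake are means (7.4.1). Section 7.4.2.2 tabulates weekly change for these three and for their sum, the SDI composite. No baseline is defined for the composite.

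**The concern.** A change from baseline should average zero in a patient who has not changed. Here it does not, for three reasons.

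- **(a) MIF.** The baseline is a best over more inhalations than the follow-up value. The change leans negative and looks like falling flow. In Weeks 1 and 2 it cannot exceed zero for any patient with use in the baseline window, because each week's best is drawn from the inhalations that define baseline.
- **(b) Weekly longest wake.** A maximum is set against a mean. The change leans positive and looks like worsening sleep, and the weekly SDI composite inherits the shift.
- **(c) Inhalation count.** This is separate from the window mismatch. A daily best rises with the number of inhalations that day, so the rows for first exceeding 4, 12 and 20 inhalations differ even if flow is constant. Matching the windows would not remove this, and the actual-value columns carry it too.

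The spurious directions in (a) and (b) are those expected before an exacerbation, and (c) ties the flow summaries to albuterol use, the study's main predictor.

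**Working it through.** The plan states no figure for this point, so there is none to reproduce. The definitions come from SAP 4.2.3, 4.2.5, 4.5, 7.2.1 and 7.4.1. Within-patient SD and frequency of use are not given. Results are therefore in within-patient SD units, assuming independent normal values unless stated.

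Let E(n) be the expected maximum of n standard normal values, by numerical integration: E(1) = 0; E(2) = 0.564; E(4) = 1.029; E(5) = 1.163; E(7) = 1.352; E(8) = 1.424; E(10) = 1.539; E(13) = 1.668; E(14) = 1.703; E(21) = 1.889; E(28) = 2.014; E(56) = 2.293; E(84) = 2.445; E(112) = 2.548; E(168) = 2.688.

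**(a) MIF, no true change.** With m inhalations a day on all 14 days, expected daily change is E(m) - E(14m) and weekly change is E(7m) - E(14m).

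- Daily, m = 1: 0 - 1.703 = -1.70
- Daily, m = 2: 0.564 - 2.014 = -1.45
- Daily, m = 4: 1.029 - 2.293 = -1.26
- Daily, m = 8: 1.424 - 2.548 = -1.12
- Daily, m = 2 with only 5 use days in the baseline window: 0.564 - 1.539 = -0.98
- Weekly, m = 1: 1.352 - 1.703 = -0.35
- Weekly, m = 8: 2.293 - 2.548 = -0.25

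Simulating 20,000 stable patients at 2 a day gave a largest Week 1 or 2 change of exactly 0.0. Under the fallback baseline of one inhalation the daily offset is 0 at 1 a day, +0.56 at 2 and +1.42 at 8.

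**(b) Weekly longest wake, no true change.** Expected change is E(nights) - 0: +1.35 with 7 valid nights and +1.03 with 4. With night-to-night AR(1) correlation of 0.3 or 0.5 it is about +1.26 or +1.15. If nightly values are lognormal with CV 0.5, 0.8 or 1.0, the weekly value is 1.77, 2.24 or 2.52 times the nightly mean. The composite shifts by the same number of minutes if its baseline is the sum of the three component baselines.

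**(c) Threshold days, no true change.** Against a fixed baseline of 2 a day on 14 days:

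- 5 inhalations: 1.163 - 2.014 = -0.85
- 13 inhalations: 1.668 - 2.014 = -0.35
- 21 inhalations: 1.889 - 2.014 = -0.12 (from unrounded values)
- Spread: 1.889 - 1.163 = 0.73

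That is the extreme case. Let counts vary instead (assumed: patient rate gamma with mean 3 a day and shape 1, day factor gamma with shape 0.7, Poisson counts, 84 days). The first days above 4, 12 and 20 then give -0.65, -0.44 and -0.38, a spread of 0.27. With half the flow variance between days they give -0.93, -0.83 and -0.80, a spread of 0.13.

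**Maximum-change summaries, read as the largest rise.** For TDS and sleep over 84 days: E(84) - 0, about +2.4. For MIF at 2 a day: E(168) - E(28) = 2.688 - 2.014 = +0.67, and about +0.7 to +0.8 with varying counts.

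**The case against.** The strongest reply is that little depends on these columns. They are descriptive, no hypothesis test uses them, and predictive modelling is reported separately (7.5.3). Actual flow values stand beside the changes, the offset cancels between rows for the same patients at stable use, and for stable patients the Week 1 and 2 rows show its size. All of that stands and keeps the point minor. It does not rescue (c), because the actual daily bests carry the same count effect.

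A reader might infer more than the documents support:

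- **That the tests of flow are distorted.** The paired comparisons in 7.5.2.1 set one seven-day window against another, so this mismatch does not enter them.
- **That MIF change is always biased downward.** The sign depends on counts. It reverses under the fallback baseline at 2 or more inhalations a day, and in the maximum-change row read as the largest rise.
- **That all sleep and step changes are affected, or that everything outside MIF and longest wake is clean.** Single-day and weekly TDS, latency and total time awake, and single-day longest wake, are sound. The maximum-change summaries in 7.2.2.1, 7.3.2.1 and 7.4.2.1 are not, because each takes an extreme over many days against baseline.
- **That 0.73 SD is the typical count effect.** It assumes a 2-a-day baseline in patients who later reach 21 inhalations. The varying-count range of 0.13 to 0.27 SD is the fairer guide.

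**Conclusion.** The point holds as a minor definitional fault in descriptive tables. The existence of the offset follows from the SAP's own definitions whenever values vary within a patient; its size does not. With use in the baseline window and stable use, MIF change is expected to be negative, and Week 1 and 2 MIF change cannot exceed zero. The SD-unit sizes rest on assumed independent normal values, use on all 14 days and seven valid nights; the threshold-day range rests on an assumed count model. Absolute size in flow units or minutes is unknown.

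Part (b) is the clearest, since 7.4.1 averages the other two SDI components and gives no reason for treating this one differently. It concerns only the wrist subset (planned n=100).

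**What to change.** 1. **Weekly longest wake.** Define it as the mean of that week's nonmissing nightly longest episodes, the rule already used for total time awake. State the SDI composite baseline as the sum of the three component baselines. Simulated null change is then within 0.001 SD.
2. **Single-day, threshold-day and weekly flow rows.** Use the mean of a day's inhalations for each flow parameter. Make baseline and Week Y the mean of those daily means over days with use only, leaving out carried-forward days. Show the actual value on the same mean basis so the paired columns reconcile, and give best-effort MIF its own actual-value row. Simulated null change is at most 0.006 SD over 80 fixed-count cases and 0.011 SD with varying counts. Setting a daily best against the mean of daily bests is not enough: with a 2-a-day baseline it gives +0.60, +1.10 and +1.32 SD on days of 5, 13 and 21 inhalations.
3. **Maximum-change summaries.** Drop them, or label them as non-zero in expectation under no change and dependent on the number of days observed. Do not apply the day-mean rule as a cure: it raises the null MIF offset from about +0.7 to about +1.75 SD.
4. **Weeks 1 and 2.** Label them as lying inside the baseline window.

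The cost is SAP wording and derivation code; all data are already collected. The flow change tables lose the best-effort reading and no longer match the maximal daily MIF tested in 7.5.2.1. A day mean includes weak inhalations and could still vary with count if flow depends on the order of inhalations within a day.
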